## 7.5 Analysis Methods

### 7.5.1 Primary Efficacy Analyses

The primary efficacy analysis will be performed on the ITT population. The primary efficacy outcome is the change from baseline (Visit 4) at Day 15 (Visit 5) in ADHD symptoms as measured by mean SKAMP-CS obtained from an average of the 7 assessments collected across the 12 hour classroom day (12 to 24 hours post-dose).

The key elements of the primary efficacy analysis are as follows:

**Data:** Change from baseline at Day 15 of mean SKAMP-CS measured on the laboratory classroom days, Visits 4 (baseline) and 5 (Day 15). Mean SKAMP-CS will be calculated by taking the average across all 7 assessment time points (8:00 am, 10:00 am, 12:00 pm, 2:00 pm, 4:00 pm, 6:00 pm, and 8:00 pm) both at baseline and at Day 15. The mean SKAMP-CS will not be rounded prior to analysis. Missing individual item data will first be imputed as described in Section 7.1.1.1 before taking the mean across all assessment time points.

**Model:** ANCOVA

**Fixed effects:** The following fixed effects are planned:

- Treatment
- Mean SKAMP-CS at baseline (Visit 4)
- Site (or pooled site if some sites to be pooled)

The null hypothesis:

$H_0$ : Change from baseline at Day 15 of the mean SKAMP-CS over all time points from 8:00 am to 8:00 pm on the laboratory classroom days are the same for dasotraline 2 mg/day and placebo

will be tested against the 2-sided alternative hypothesis:

H1: Change from baseline at Day 15 of the mean SKAMP-CS over all time points from 8:00 am to 8:00 pm on the laboratory classroom days are not the same for dasotraline 2 mg/day and placebo.

The average treatment difference over all post-dose time points will be estimated using LS means from the ANCOVA. The treatment comparison will be conducted as a 2-sided test at the 5% level of significance. The standard error and 95% confidence interval for the treatment difference as well as the treatment effect size will be provided. Effect size will be calculated as the absolute value of the LS mean treatment difference divided by the observed pooled standard deviation, which will be calculated using the following formula:

$$SD = SE(\bar{x}_d) / \sqrt{1/N_{PBO} + 1/N_{DAS}}, \text{ where } \bar{x}_d \text{ is the LS mean treatment difference.}$$

The estimand of this primary efficacy analysis is the LS mean treatment difference, Dasotraline 2mg vs. placebo, of mean change from baseline in mean SKAMP-CS among all randomized subjects who remain in the study for the duration of the two-week double-blind period, regardless of treatment adherence.

The primary efficacy analysis will also be repeated for the per protocol (PP) population.

### 7.5.2 Secondary Efficacy Analyses

The secondary efficacy outcomes include:

- Mean SKAMP-Combined score from the 7 assessments collected across the 12-hour classroom day (12 to 24 hours post-dose) on Day 15
- SKAMP-Combined score at each of the assessment times (12-, 14-, 16-, 18-, 20-, 22-, and 24-hours post-dose) during the classroom day on Day 15
- Change from baseline at Day 15 in SKAMP-Combined score at each of the assessment times (12-, 14-, 16-, 18-, 20-, 22-, and 24-hours post-dose) during the classroom day
- Change from baseline at Day 15 in mean SKAMP-Attention subscale score obtained from the 7 assessments collected across the 12-hour classroom day (12 to 24 hours post-dose)
- SKAMP-Attention subscale score at each of the assessment times (12-, 14-, 16-, 18-, 20-, 22-, and 24-hours post-dose) during the classroom day on Day 15

- Change from baseline at Day 15 in SKAMP-Attention subscale score at each of the assessment times (12-, 14-, 16-, 18-, 20-, 22-, and 24-hours post-dose) during the classroom day
- Change from baseline at Day 15 in mean SKAMP-Deportment subscale score obtained from the 7 assessments collected across the 12-hour classroom day (12 to 24 hours post-dose)
- SKAMP-Deportment subscale score at each of the assessment times (12-, 14-, 16-, 18-, 20-, 22-, and 24-hours post-dose) during the classroom day on Day 15
- Change from baseline at Day 15 in SKAMP-Deportment subscale score at each of the assessment times (12-, 14-, 16-, 18-, 20-, 22-, and 24-hours post-dose) during the classroom day
- Change from baseline at Day 15 in Permanent Product Measure of Performance (PERMP)-Attempted and Correct Problems scores at each of the assessment times (12-, 14-, 16-, 18-, 20-, 22-, and 24-hours post-dose) during the classroom day
- PERMP-Attempted and Correct Problems scores at each of the assessment times (12-, 14-, 16-, 18-, 20-, 22-, and 24-hours post-dose) during the classroom day on Day 15
- Change from baseline at Day 15 in mean PERMP-Attempted score obtained from an average of the 7 assessments collected across the 12-hour classroom day (12 to 24 hours postdose).
- Change from baseline at Day 15 in mean PERMP-Correct score obtained from an average of the 7 assessments collected across the 12-hour classroom day (12 to 24 hours postdose).
- Change from baseline at Day 15 in mean PERMP total score (PERMP-Attempted + PERMP-Correct) obtained from the 7 assessments collected across the 12-hour classroom day (12 to 24 hours post-dose)

Secondary weight-adjusted dose-level efficacy analyses will also be conducted on the SKAMP. See section 10 for details.

For secondary efficacy outcomes of mean SKAMP-Attention subscale scores, mean SKAMP-Deportment subscale scores, mean PERMP-A, mean PERMP-C, and mean PERMP total score, missing time points will be handled as follows:

If 3 or more time points have missing or invalid scores, the mean score will be set to

missing. If one or two time points have a missing or invalid score, the mean score will be calculated as the average of the scores at the remaining time points. Missing individual items will not be imputed.

Descriptive statistics for the SKAMP-CS, SKAMP-Attention subscale scores, SKAMP-Depression subscale scores, PERMP-A, PERMP-C, and PERMP total scores will be calculated for the change from baseline (Visit 4) at Day 15 (Visit 5), average across all time points and for each time point individually for the laboratory classroom day on Day 15, and will be presented for each treatment as well for the differences between the treatments (dasotraline 2 mg/day vs. placebo) based on the ITT population.

In addition, the secondary SKAMP and PERMP efficacy variables will be analyzed based on a similar ANCOVA model to the one described above for the ITT population. These models will mirror the model used in the primary analysis, with the relevant SKAMP/PERMP score at baseline as a fixed effect in place of the mean SKAMP-CS at baseline.

The observed means, LS means and associated standard error bars will be plotted over time for SKAMP-CS and the PERMP scores for the laboratory classroom day at Baseline (Visit 4) and Day 15 (Visit 5) by treatment group. Change from baseline SKAMP-CS, change from baseline SKAMP subscale scores, and change from baseline PERMP scores will be plotted over time at Day 15 (Visit 5) by treatment group, as well as by subgroup (sex, race, age).

### **7.5.3 Examination of Subgroups**

The primary efficacy analyses will be repeated on the ITT population based on the following subgroups:

- Sex (Male and Female)
- Race (White, Black or African American, and Other)
- Age (6-9 years and 10-12 years)
- Previous treatment (stimulant and treatment-naïve)

The interaction of each subgroup with the treatment effect will also be measured. The primary efficacy analysis will be repeated on the ITT population once for each subgroup above, with the subgroup of interest added as a fixed effect, along with the interaction between the subgroup of interest and the treatment effect. The p-values from the resulting tests for interaction will be summarized.

## **8. SAFETY EVALUATION**

All safety analyses will be performed on the safety population. All subjects who were randomized and received at least 1 dose of study medication will be assessed for safety. Safety will be monitored by physical and neurological examinations, vital signs, AEs assessed at each visit, electrocardiography, and clinical laboratory tests. In addition, the C-SSRS will be administered at Screening (Visit 1) and all subsequently scheduled visits to assess emergent suicidal thoughts or behaviors.

### **8.1 Overview of Safety Analysis Issues**

Missing end dates for AEs will not be imputed. If end date information is not available, it will be assumed that the finding or event is ongoing.

Missing AE start dates will be imputed based on the following rules:

- If only the year is known, the date will be set to 01 January of that year. If the year is the same as the year of the first dose of study medication, the date will be set to the date of the first dose of study medication.
- If the year and day are known, the date will be set to January of that year. If the year and day is the same as the year and day of the first dose of study medication, the date will be set to the date of the first dose of study medication.
- If the year and month are known, the date will be set to first day of the month. If the year and month are the same as the year and month of the first dose of study medication, the date will be set to the date of the first dose of study medication.
- If the start date is completely missing, it will be set to the date of the first dose of study medication.

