### 8.4 Adverse Events

All AEs will be coded using MedDRA Version 19.0. An AE is any untoward medical occurrence:

- that occurred on or after the first dose of study medication,
- with a missing start date and a stop date on or after the first dose of study medication, or
- with both a missing start and stop date.

Untoward medical occurrences that occur between the time of informed consent/assent and first study drug administration are pre-treatment events. Those that occur after first administration of study drug are considered AEs. Clinically significant abnormal objective findings (eg, clinical laboratory value, ECG value, and physical examination observation) will also be recorded as AEs.

A serious adverse event (SAE) is an AE that meets one or more of the following criteria:

- Results in death.
- Is life threatening.
- Requires hospitalization or prolongation of existing hospitalization.
- Results in persistent or significant disability or incapacity.
- Is a congenital anomaly or birth defect.
- Is an important medical event that may jeopardize the subject or may require a medical or surgical intervention to prevent one of the outcomes listed

above. Examples of such medical events include allergic bronchospasm requiring intensive treatment in an emergency room or at home, blood dyscrasias or convulsions that do not result in inpatient hospitalization.

An AE is considered treatment emergent if it started during or after administration of the first dose of study medication, and started on or prior to the day of the subject's final visit (including the follow-up visit). In addition, medical history events that worsen in severity after the start of dosing will be considered treatment-emergent adverse events (TEAEs). AEs with partial start dates will be imputed as outlined in Section 8.1 and assigned to the associated treatment period.

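### The SAP's rule for AE start dates with a missing month imputes January, so nearly all such on-treatment events lose treatment-emergent status

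*SAP*

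**What the plan says.** SAP 8.1 introduces its list with "Missing AE start dates will be imputed based on the following rules". In paraphrase, with the key wording quoted, the rules are:

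- **Year only:** 1 January. The first-dose date is used instead "If the year is the same as the year of the first dose of study medication".
- **Year and day, month missing:** "If the year and day are known, the date will be set to January of that year". The first-dose date is used instead only "If the year and day is the same as the year and day of the first dose of study medication".
- **Year and month, day missing:** first of the month, or the first-dose date if year and month both match the first dose.
- **Nothing known:** "If the start date is completely missing, it will be set to the date of the first dose of study medication".

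SAP 8.4 makes these dates decisive: "An AE is considered treatment emergent if it started during or after administration of the first dose of study medication", provided that it also started no later than the final visit. It adds: "AEs with partial start dates will be imputed as outlined in Section 8.1 and assigned to the associated treatment period".

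SAP 8.4 also says when an occurrence without a start date counts as an AE. One route is "with a missing start date and a stop date on or after the first dose of study medication, or"; the other is that both dates are missing. Protocol 15.3.6.1 gives the same conditions.

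**The concern.** Three of the four rules lean the same way: if the known part of the date is compatible with the dosing date, the event is placed on the first dose and counted. The missing-month rule does the opposite. It places the event in January, before dosing for almost every child first dosed later in the year. A site that records the day as well as the year thus gets a less conservative result than one that records the year alone. That is hard to see as a deliberate choice.

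At stake are the TEAE summaries in SAP 8.4: the overall count, the tables by system organ class and preferred term, and those for severity, relationship and discontinuation. An affected event leaves all of them. Its onset relative to the first dose, as listed, is also wrong. The error runs against detecting harm.

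**Working it through.** The plan states no figure for this rule, so there is none to reproduce. The check applies the SAP 8.1 rule literally and then the SAP 8.4 test.

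**Inputs**

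- Imputation rule and exception: SAP 8.1.
- TEAE test, imputed start not before first dose: SAP 8.4.
- Follow-up: Day 1 to about Day 21, so 21 onset days (Protocol Table 2; SAP 14.1).
- Longest screening window: 42 days (SAP 2.2) or 35 days (Protocol 7.1).
- Assumption: every first-dose date in a 365-day year is equally likely, and so is every onset day. Two such years (2017 and 2018) are counted.

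**One child.** Take a first dose on 12 September 2017 and delete the month from the true onset.

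| True onset | Imputed start | Days from first dose | TEAE? |
|---|---|---|---|
| 12 Sep | 12 Sep (exception) | 0 | yes |
| 15 Sep | 15 Jan | -240 | no |
| 26 Sep | 26 Jan | -229 | no |
| 2 Oct | 2 Jan | -253 | no |

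The three January dates also lie far outside the 42-day screening window.

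**All first-dose dates, per year**

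- *February to November:* 365 - 62 = 303 dates. Any January date precedes the dose, and only the onset on the dose's own day-of-month is rescued. Lost: 303 × 20 = 6,060 of 303 × 21 = 6,363, or 20/21 = 95.2%.
- *December:* onsets that cross into the next year keep a correct January date. For doses on 1 to 11 December, 11 × 20 = 220 are lost; for 12 to 31 December, 19 + 18 + ... + 0 = 190. Total 410 of 31 × 21 = 651, or 63.0%.
- *January:* January onsets are imputed correctly and only February onsets are lost. For doses on 12 to 31 January, 1 + 2 + ... + 20 = 210 of 651, or 32.3%.
- *Whole year:* 6,060 + 410 + 210 = 6,680 of 365 × 21 = 7,665. Over two years this is 13,360 of 15,330, or 87.1%.

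These are shares of on-treatment events whose record has day and year but no month.

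**With a corrected rule.** Taking the earliest date in the recorded year that has the recorded day and is not before the first dose leaves 0 of 15,330 before dosing.

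**Stop dates and partial starts.** Suppose the start is recorded as September 2017 with the day missing, the stop is 5 September and the first dose is 12 September. Year and month match, so SAP 8.1 sets the start to 12 September, 7 days after the stop. A start recorded only as 2017 gives the same result. SAP 8.1 has no stop-date check, and the SAP 8.4 condition speaks of a missing start date, not a partial one.

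**The case against.** **Rarity.** The defect needs a record with day and year but no month. AEs are recorded at two visits, about Day 15 and Day 21 (Protocol 11.5). Data queries run in the EDC system (Protocol 16.1), monitors check CRFs for completeness (16.3), and lock requires that no data issues are outstanding (SAP 4). This stands: such records should be few. It limits the effect but does not correct the rule.

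**Limited reach.** Safety analyses are descriptive (SAP 8.2), so no test depends on this. The SAE tables, the tables of AEs leading to death and the listing of all AEs are not restricted to TEAEs. This also stands; the loss is from the TEAE tables.

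**An error in both directions?** A reader might infer that SAP 8.1 also turns pre-treatment events with no start date into TEAEs, in conflict with SAP 8.4. The documents do not support this. SAP 8.4 and Protocol 15.3.6.1 count an occurrence with a missing start date as an AE only if its stop date is on or after the first dose, or is missing too. An event known to have ended before dosing is thus not an AE, and the rule for AE start dates does not reach it. Counting events with both dates missing is a deliberate conservative default.

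**Partial dates already covered?** SAP 8.1 puts partial dates under its heading for missing ones, so the SAP 8.4 stop-date condition could be read to cover them. But SAP 8.4 itself refers separately to partial start dates and sends them to SAP 8.1, which has no such condition. The gap is small and best closed in words.

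**Conclusion.** The missing-month rule in SAP 8.1 is wrong as written, and no other section of the SAP or protocol corrects it. For first doses in February to November it removes TEAE status from 20 of 21 on-treatment onset days among month-missing records; the share is 63.0% for December, 32.3% for January and 87.1% over the year. The percentages assume uniform dosing and onset dates and a 21-day window. The February-to-November result does not depend on how dosing dates are spread over those months.

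The absolute effect cannot be sized, because the documents do not say how many AEs have a day and year but no month. It is probably small, so this is a minor point, but its direction is anti-conservative. The absent stop-date check for partial dates is secondary. The handling of completely missing start dates needs no change.

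**What to change.** In SAP 8.1, replace the exception to the missing-month rule: if the year equals the year of first dose and the month is missing, set the start to the first-dose date, unless the stop date is before the first dose, in which case the event is pre-treatment.

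A finer alternative, under the same stop-date condition, is the date with the recorded day that falls between first dose and final visit. With about 21 days of follow-up there is at most one such date. If there is none, use the first-dose date.

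Add the same stop-date condition to the year-only and year-plus-month rules, so that no imputed start falls after a known stop.

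The cost is a line or two of SAP text and trivial programming, with no change to data collection. It should be done before unblinding.

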### **8.2 Overview of Safety Analysis Methods**

Safety data will be analyzed descriptively using the safety population described in Section 4.2. Unless specified, all safety summaries will be presented by descriptive statistics, such as number of subjects (n) and percentage for categorical variables and number of subjects (n), mean, standard deviation, median, minimum, and maximum for continuous variables.

### 8.3 Extent of Exposure

The length of exposure (in days) of study medication will be calculated based on the dates of first and last dosing of study medication (last dosing date - first dosing date + 1). Length of exposure will be summarized by treatment group on the safety population as continuous values.

For subjects lost to follow-up, no imputation of the length of exposure will be conducted. For subjects who discontinue the study early but return for a follow-up visit, the follow-up data will be used to calculate the length of exposure.

### 8.4 Adverse Events

All AEs will be coded using MedDRA Version 19.0. An AE is any untoward medical occurrence:

- that occurred on or after the first dose of study medication,
- with a missing start date and a stop date on or after the first dose of study medication, or
- with both a missing start and stop date.

Untoward medical occurrences that occur between the time of informed consent/assent and first study drug administration are pre-treatment events. Those that occur after first administration of study drug are considered AEs. Clinically significant abnormal objective findings (eg, clinical laboratory value, ECG value, and physical examination observation) will also be recorded as AEs.

A serious adverse event (SAE) is an AE that meets one or more of the following criteria:

- Results in death.
- Is life threatening.
- Requires hospitalization or prolongation of existing hospitalization.
- Results in persistent or significant disability or incapacity.
- Is a congenital anomaly or birth defect.
- Is an important medical event that may jeopardize the subject or may require a medical or surgical intervention to prevent one of the outcomes listed

above. Examples of such medical events include allergic bronchospasm requiring intensive treatment in an emergency room or at home, blood dyscrasias or convulsions that do not result in inpatient hospitalization.

An AE is considered treatment emergent if it started during or after administration of the first dose of study medication, and started on or prior to the day of the subject's final visit (including the follow-up visit). In addition, medical history events that worsen in severity after the start of dosing will be considered treatment-emergent adverse events (TEAEs). AEs with partial start dates will be imputed as outlined in Section 8.1 and assigned to the associated treatment period.

### **Summary Tabulations**

An overview of the frequency, i.e., the number and percentage of subjects and events with at least one of the following AEs, will be presented by treatment group (placebo, dasotraline 2 mg/day, and total):

- All TEAEs
- SAEs
- TEAEs leading to discontinuation
- Severe TEAEs
- TEAEs related to study medication
- SAEs related to study medication
- AEs leading to death

### **System Organ Class and Preferred Term Tabulations**

The frequency of subjects reporting TEAEs, along with the frequency of events, will be summarized within each system organ class (SOC) and preferred term (PT) by treatment group. The SOC terms and PTs will be presented in decreasing order of the total number of subjects (frequency) who experienced each AE. System organ class terms and PTs with the same frequency will be presented alphabetically.

Each subject will be counted only once within each SOC and within each PT. If a single subject experienced the same AE more than once within a treatment period, the subject will be counted once per SOC and PT for that AE. For subjects that experienced AEs with multiple severities, the AE with the highest known severity within each SOC and PT

will be counted. Adverse events with unassigned/unknown severity will be categorized as severe.

For summaries by relationship to the study medication, AEs will be grouped as “related” or “not related.” AEs assessed as “possible,” “probable,” or “definite,” will be grouped as “related.” If a subject reports more than one AE within the same treatment regimen, SOC and PT, and any are related, it will be summarized as related. AEs whose relationship to treatment is assessed as “not related” or “unlikely” will be grouped as “not related.” Events with unassigned/unknown relationship to study medication will be considered related to study medication.

The frequency of subjects reporting the following AEs, along with the frequency of events, will be summarized and presented by treatment group and MedDRA SOC and PT for the Safety population:

- All TEAEs (including number of events and subject incidence)
- SAEs
- Non-SAEs (including number of events and subject incidence)
- TEAEs leading to discontinuation
- TEAEs by maximum severity (mild, moderate, severe)
- TEAEs by relationship to the study treatment (related, or not related)
- SAEs by relationship to the study treatment
- AEs leading to death
- AEs during the treatment period
- AEs during the follow-up period (defined as any AE occurring after treatment stop date + 7 days)

